To determine if the intraocular pseudophakic contact lens (IOPCL), referred to as the AccuraSee, provides refractive correction using a plus powered lens in subjects with ocular pathology previously implanted with a Bausch and Lomb LI61AO or LI61SE monofocal posterior chamber intraocular lens (PCIOL) and to confirm its positional stability and adherence relative to the PCIOL.

Study Design:

This will be a 12-month three center study, in which a maximum of 10 pseudophakic subjects will be enrolled.

This study is being conducted in accordance with 21 CFR Parts 50, 54, 56 and 812.42 (U.S.C 282(j)). ISO 14155 Clinical investigation of Medical Devices for Human Subjects, ISO 11979-7, and the ethical principles laid down in the Declaration of Helsinki.

1. Introduction and Rationale

The AccuraSee (intraocular pseudophakic contact lens) consists of a 4.5 mm diameter concave-convex optic with three opposing haptic straps, or tabs. The haptic straps are designed to enter and rest within three channels created under the anterior leaflet of the capsular bag. Each channel is created with a Cady-Soiseth Capsule Separator spatula. Each haptic strap or tab has a small pawl, or ridge on the bottom that is used to catch and lock on to the IOL optic edge. This pawl aids in both centering the AccuraSee on the IOL optic as well as allowing the haptic strap to stay securely seated while contained under the surface tension of the anterior leaflet of the capsular bag. The lens is designed to fine-tune the residual refractive error of the longstanding pseudophakic eye. The lens design, position and surgical approach are intended to lessen the complication rate and overall invasive nature of today's available secondary lens implantation technologies.

2. Study Objective

The primary objective of this study is to determine the stability of the AccuraSee to successfully adhere to a pseudophakic intraocular lens without rotation or slippage.

The secondary objective of this study is to determine if the AccuraSee can successfully change refraction up to +3.0 diopters (D) in subjects previously implanted with an Bausch and Lomb LI61AO and LI61SE monofocal intraocular lens.

Safety Endpoints

- Preservation of BCDVA Proportion of eyes (< 5%) that lose two or more lines of BCDVA from baseline.
- Successful delivery of the IOPCL as determined at 7-14 days post-operative
 - o No capsular tear
 - o Visualize centration between the PCIOL and IOPCL
 - o No visible damage to either the PCIOL or the IOPCL
 - o Uniform leaflet coverage of all IOPCL haptic tabs
- Long-term adherence and positional stability
 - Minimal Change in uniformity of the gap between 1-2 months and 4-6-months as determined by UBM measurements. Minimal change is defined as +/- 10 microns between visits is established and maintained using UBM imaging
- Characterization and incidence of cumulative and persistent intraoperative and post-operative adverse events.

Stopping Rules

The Sponsor or the clinical investigator can suggest suspension of the clinical trial at any time if they are in receipt of information that leads them to believe that continuing the study jeopardizes the health and welfare of the clinical trial participants. Suspension of the study will be considered if two or more consecutive severe ocular injuries occur at any one clinical site that are related to the surgical procedure and/or IOPCL device. A severe ocular injury results in a permanent impairment of a vision or permanent damage to an eye.

Examples:

- Uveitis-Glaucoma-Hyphema (UGH) Syndrome. Intraocular chafing from the IOL/PCIOL implant leading to a spectrum of iris transillumination defects and pigmentary dispersion to microhyphemas with elevated intraocular pressure.
- Posterior capsule rupture with IOL/PCIOL dislocation resulting in a posterior vitrectomy during the surgical procedure

Primary Effectiveness Endpoint

Proportion of eyes ($\geq 50\%$) able to achieve a stable target refraction, (manifest or autorefraction) within 0.5 D of the intended target. Stability is achieved when there is no change (± 0.50 D) within two consecutive postoperative visits at 1 month or later visits.

04-08-2021 5

3. Subject Population

A maximum of 10 pseudophakic eyes will be implanted unilaterally with the AccuraSee IOPCL.

3.1. Inclusion Criteria:

- 1. Subjects who have already had cataract surgery with a Bausch and Lomb monofocal intraocular lens model LI61A0 (with lens power from 18.0 diopters (D) to 23.0 D) or model LI61SE (with a lens power from18.0 D to 22.5 D), as clearly evidenced by photographic documentation with one of the following: (1) patient medical record, (2) clinic chart with labeling attached, (3) surgical record with labeling attached, or (4) patient identification card with make, model, power, and serial number.
- 2. Able to comprehend and sign a statement of informed consent.
- 3. Willing and able to complete all required postoperative visits.
- 4. Subjects who's baseline MRSE is between -0.5D and +3.0D
- 5. Best corrected visual acuity 20/80 or worse.
- 6. Subjects with $\leq 1.5D$ of corneal cylinder
- 7. Subjects willing to abstain from pursuing any other surgical vision-correcting procedures for the duration of the study.
- 8. Subject must be at least 22 years or older.

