3.2 Safety Endpoints

Preservation of Best Corrected Distance Visual Acuity (BCDVA)

The preservation of BCDVA is defined as proportion of eyes (< 5%) that lose two or more lines of BCDVA from baseline.

• Successful Delivery of the IOPCL as determined at 7-14 days post-operative

The successful delivery of the IOPCL is defined as no capsular tear, visualize centration between the IOL and IOPCL, no visible damage to either the IOL or IOPCL, and uniform leaflet coverage of all IOPCL haptic tabs.

• Long-term Adherence and Positional Stability

The long-term adherence and positional stability is defined as minimal change (i.e. \pm 10 microns) between 1-2 months and 4-6- months as determined by UBM measurements. The open central spacing between the IOL and IOPCL is established and maintained using UBM imaging.

Adverse Events

The Adverse Events is defined as characterization and incidence of cumulative and persistent intraoperative and post-operative adverse events.

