7.5.3 Long-term Adherence and Positional Stability

The analysis of this clinical outcome will be based on the observed data of AccuraSee IOPCL. The number and percent of eyes with minimal change (i.e. \pm 10 microns) between 1-2 months and 4-6- months established and maintained central spacing between the IOPCL and IOL will be reported.

Long-term adherence and positional stability will also be stratified by the surgical technique (e.g., discrete narrow channels or wider sweeping channels).

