8 CHANGES FROM PLANNED ANALYSES

8.1 Changes from the Original Protocol

Version 2.0 – None

Version 3.0 – Add subgroup analyses for effectiveness due to the first 3 eyes having poor preoperative BCDVA with underlying pathology.

Version 4.0 – Updated study objective to match clinical study protocol. Add effectiveness analysis using autorefraction measurements. Revised subgroup analyses for effectiveness to subjects having poor preoperative BCDVA with underlaying pathology (removed first 3 eyes language).

Version 5.0 – Added analysis to evaluate the impact of surgical technique on IOPCL stability.

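### The long-term UBM stability result stops at the 4-6 month visit although a 12-month UBM is scheduled, and the Protocol and SAP word its limit for different quantities

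*Protocol*

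**What the plan says.** Protocol section 2 and SAP section 2 give the same primary objective: to "determine the stability of the AccuraSee to successfully adhere to a pseudophakic intraocular lens without rotation or slippage".

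The related endpoint is listed among the safety endpoints.

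- Protocol section 2, Safety Endpoints: "Minimal Change in uniformity of the gap between 1-2 months and 4-6-months as determined by UBM measurements", followed by "Minimal change is defined as +/- 10 microns between visits is established and maintained using UBM imaging".
- SAP 3.2: "The long-term adherence and positional stability is defined as minimal change", with the same ±10 microns and the same two visits. A separate sentence adds: "The open central spacing between the IOL and IOPCL is established and maintained using UBM imaging".
- SAP 7.5.3 counts eyes within ±10 microns between those two visits, with "established and maintained central spacing between the IOPCL and IOL will be reported". It continues: "Long-term adherence and positional stability will also be stratified by the surgical technique". SAP 8.1 records that split under Version 5.0: "Added analysis to evaluate the impact of surgical technique on IOPCL stability".

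Protocol section 11 schedules UBM at 30-60, 120-180 and 330-420 days, and at interim visits. SAP 6.8 sets an interim analysis around the 4-6 month visit and the final analysis after 12 months of follow-up. SAP 4 ties an IDE submission to the 4-6 month outcomes.

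**The concern.** An endpoint labelled long-term is closed at the second of three scheduled UBM visits. The 4-6 month cut suits the interim analysis and the submission, but it does not explain why the final report leaves out the last reading. If the lens moved between Form 4 and Form 5, the only planned trace would be an adverse event term. A gradual change in spacing that nobody recorded as an event would not be reported. Under SAP 6.1, a 12-month comparison added later would count as exploratory and be reported as post hoc or as a change to the plan.

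The second matter is wording. The Protocol attaches ±10 microns to gap uniformity, which the text available does not define. The SAP counts central spacing. If uniformity meant evenness of the gap across the optic, the two could classify the same eye differently.

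**Working it through.** **Is the 12-month UBM used anywhere?** I looked in each place where it could appear.

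- Protocol section 2 and SAP 3.2: the endpoint names 1-2 and 4-6 months only.
- SAP 3.2, the central-spacing sentence: it has no time limit, but it sets no comparison either.
- SAP 7.5.3: counts eyes between the same two visits.
- SAP 3.3 and 7.5.5 (other outcomes and other safety analyses): UBM is not listed.
- SAP 6.8: sets the final analysis at 12 months without naming UBM.

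So two of the three scheduled UBM visits are used, and no analysis is named for the third.

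**How much follow-up does this leave out?** The visit windows come from Protocol section 10: Form 3 at 30-60 days, Form 4 at 120-180, Form 5 at 330-420. The shortest span is the earliest later visit minus the latest earlier visit. The longest span is the reverse.

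| Comparison | Shortest | Longest |
|---|---|---|
| Form 3 to Form 4 (planned) | 120 − 60 = 60 days | 180 − 30 = 150 days |
| Form 4 to Form 5 (no UBM analysis) | 330 − 180 = 150 days | 420 − 120 = 300 days |
| Form 3 to Form 5 (available) | 330 − 60 = 270 days | 420 − 30 = 390 days |

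As a share of one eye's span from Form 3 to Form 5, the planned comparison covers between (120 − 60)/(420 − 60) = 60/360 = 17% and (180 − 30)/(330 − 30) = 150/300 = 50%.

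**What does one eye weigh?** SAP 6.2 caps the study at 10 eyes, and SAP 6.5 uses available data without imputation. One eye is 1/10 = 10 points, or 1/8 = 12.5 points if, as an example, 8 eyes have both readings. If both technique groups in SAP 7.5.3 contain eyes, the smaller has at most 5, so one eye there is at least 1/5 = 20 points. Neither document sets a target proportion for this endpoint.

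**Do the two quantities differ?** The Protocol's limit sentence does not parse: "Minimal change is defined as +/- 10 microns between visits is established and maintained using UBM imaging". The SAP 3.2 sentence ends in the same words but has its subject: "The open central spacing between the IOL and IOPCL is established and maintained using UBM imaging". The likeliest explanation is that the Protocol sentence lost that subject, and that uniformity there means constancy between visits. On that reading the documents agree. The text available does not settle it.

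**The case against.** The case for leaving the plan alone has several sound parts.

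- **The window is a consistent choice.** Both documents use the same two visits, and these fit the 4-6 month analysis and submission. A 12-month reading could not inform that submission. This stands: the point is an omission from the final report, not a contradiction.
- **Late failure is still captured.** Protocol section 12 lists dislocation, malposition (with a late category from 120 days) and unseated tabs, and SAP 7.5.4 summarises events at each visit. This stands too, so it would be wrong to infer that position goes unmonitored after six months. What is missing is the UBM measurement.
- **The post hoc label costs little here.** The analyses are descriptive, and SAP section 1 allows amendment before database lock. That is true, and it also makes the amendment easy.
- **The SAP governs the analysis.** Protocol section 16 says so, and SAP 7.5.3 names central spacing.

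Two stronger readings are tempting. The first is that the documents hold two conflicting stability endpoints. That requires uniformity to mean evenness across the optic, which the text does not say, and the matching sentence endings point the other way. Measurement details may also sit in Appendices 3 and 8, which were not available.

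The second is that rotation, named in the primary objective, is not measured at all. No postoperative rotation reading or analysis appears in the text available. However, Appendices 2A, 3 and 8 were not seen, slit-lamp findings are summarised by visit (SAP 7.5.5.3), and the operative video may document the initial orientation. Absence cannot be concluded.

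**Conclusion.** The point holds as a gap in the planned analysis plus a wording mismatch. As written, the final report would give no UBM stability result beyond 4-6 months. Its only UBM comparison would span 60 to 150 days, although scheduled images allow 270 to 390 days. The Protocol and SAP should also name the same quantity for the ±10 micron limit; the mismatch is probably a drafting loss in the Protocol.

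The consequence is limited. The study is an early feasibility study of at most 10 eyes, and with no pass mark a changed classification alters the reported rate but reverses no success verdict. The finding rests on the visit windows as stated and on the named analyses in the SAP text. Calling this the endpoint closest to the primary objective is my reading: the documents list it as one of four safety endpoints and do not rank them. The rotation question is secondary and does not carry the conclusion.

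**What to change.** 1. In SAP 3.2 and 7.5.3, keep Form 3 to Form 4 for the interim analysis. Add, by amendment before database lock, the count and percentage of eyes within ±10 microns from Form 3 to Form 5 as the 12-month stability result, with the same split by surgical technique. Show the denominator and, beside the rate, list dislocation, malposition and unseated-tab events by eye. Under SAP 6.5 an eye without both readings drops out of the percentage, so the listing keeps such eyes visible.
2. Reconcile Protocol section 2 with SAP 3.2 and 7.5.3 so that the limit applies to one named UBM quantity. The SAP currently says central spacing; the sponsor should confirm it.
3. As a secondary matter, check whether the case report forms record lens orientation after surgery. If they do not, the report should state that rotation was not assessed.

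The cost is a wording change in two documents and a few more descriptive rows and listings. Item 1 uses UBM readings already scheduled. The sponsor should expect that the 12-month rate may be lower than the 4-6 month rate.

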- ➤ Malpositioned/Misaligned Optics (IOPCL not centered over PCIOL)
 - o Early[1]
 - o Late[2]
- Unseated IOPCL haptic tabs (One or more haptic tabs not securely attached to the PCIOL)

- > Post Nd:YAG Posterior capsulotomy event
- > Lens Optical Performance
- Mechanical Failure
- Vitreous Aspiration for Pupillary Block
- Corneal Stroma Edema
 - Corneal Edema with BCDVA of 20/40 or worse at Form 3 (1-2M post-op) or later
- > Iritis present at 1-month or later
- Macular Edema present at 1-month or later
- > Raised IOP requiring treatment
 - Raised IOP, greater than 10 mmHg above baseline and to a minimum of 25 mmHg.
- ➤ Iris Chafing
- > Iris Trauma and/or Damage
- > Iris Transillumination Defects
- > Pigment Dispersion
- > Pseudophacodonesis or Evidence of Zonular Trauma/dehiscence
- > Inter-device opacification or fibrosis between the PCIOL and IOPCL
- > Other

```
[1]Early – prior to Form 4 visit window (i.e., < 120 days)
[2]Late – At 120 days or later
```

Note: Secondary Surgical Intervention(s) (SSI) may be necessary to resolve any of the adverse events identified above. If an SSI is conducted in the trial, the details of the SSI and corresponding reason for SSI will be documented on the SSI CRF.

Examples of Secondary Surgical Interventions

- ➤ Irrigation of IOPCL/IOL Interface
- > Exchange
- ➤ Reposition of the same Implantable Pseudophakic Contact Lens
- ➤ Removal

13. Adverse Experience and Complication Reporting

Throughout the course of the proposed study, all efforts will be made to remain alert to possible adverse experiences or untoward findings. If adverse experiences occur, the first concern will be the safety and welfare of the subject and appropriate medical intervention will be made. Any adverse experiences observed by the investigator or reported by the subjects, whether or not ascribed to the investigational procedure or device, will be recorded on the subjects' adverse event case report form. A new adverse event case report form is used for each adverse event or adverse event related visit.

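### The long-term positional stability endpoint has no decentration or rotation criterion, so under the SAP a slipped lens can count as stable, although the primary objective concerns rotation and slippage

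*Protocol*

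**What the plan says.** Protocol section 2 and SAP section 2 give the same primary objective: to "determine the stability of the AccuraSee to successfully adhere to a pseudophakic intraocular lens without rotation or slippage".

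Two safety endpoints in protocol section 2 concern position.

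- **Delivery.** This is "Successful delivery of the IOPCL as determined at 7-14 days post-operative". Its components include "Visualize centration between the PCIOL and IOPCL" and capsular leaflet cover over every tab. SAP 3.2 repeats it with the same timing.
- **Long-term adherence and positional stability.** The protocol asks for "Minimal Change in uniformity of the gap between 1-2 months and 4-6-months as determined by UBM measurements", and adds: "Minimal change is defined as +/- 10 microns between visits is established and maintained using UBM imaging". SAP 3.2 instead speaks of the open central space between the two lenses. SAP 7.5.3 says that the number and percent of eyes with minimal change and with "established and maintained central spacing between the IOPCL and IOL will be reported".

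Protocol section 12 lists "Malpositioned/Misaligned Optics (IOPCL not centered over PCIOL" as a postoperative adverse event, split into early and late at 120 days. IOPCL dislocation and unseated haptic tabs are also listed. Under protocol section 11, adverse events are collected and slit-lamp examination is done at every postoperative visit to 12 months. SAP 7.5.4 tabulates each event by visit and cumulatively. UBM is scheduled at Forms 3, 4 and 5.

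**The concern.** Slippage of one optic over another is movement across the optical axis, and rotation is movement about it. The measure that the SAP counts is a distance along the axis. The endpoint criteria that would see sideways movement directly, centration and leaflet cover, belong to the delivery endpoint at 7-14 days and are not part of the later stability count.

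The rate that answers the primary objective may therefore be insensitive to the failure that the objective names. The stability table and the adverse event table could also disagree about the same eye, with no rule for which one answers the objective. SAP 7.5.3 stratifies stability by surgical technique, so a difference in decentration between techniques could go unseen there as well.

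**Working it through.** There is no stated figure to reproduce. The sample size is a cap of 10 eyes without a calculation, and the point is about how the endpoint is defined.

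**Step 1. What each measure can detect.**

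| Measure | When | Sideways shift | Rotation | Enters the stability count |
|---|---|---|---|---|
| Centration and leaflet cover (delivery) | 7-14 days | Yes, by eye, no distance limit | Not addressed | No |
| Uniformity of gap (protocol) | 1-2 vs 4-6 months | Possibly | Need not | Yes, under the protocol |
| Central spacing (SAP) | 1-2 vs 4-6 months | Weakly | Need not | Yes, under the SAP |
| Malposition, unseated tabs, dislocation (adverse events) | Every postoperative visit | Yes, if noticed, no distance limit | Not addressed as such | No |

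**Step 2. Sideways shift and the 10-micron limit (illustration).** Inputs: limit 0.010 mm (protocol section 2, SAP 3.2), optic diameter 4.5 mm and so half-width 2.25 mm (protocol section 1), and a radius of curvature R of the back surface of the IOPCL. R is not in the documents. It is assumed to be 8 to 20 mm, with 30 mm as an outer case. The lens is assumed to shift by d in its own plane, without tilt.

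- Change in central gap ≈ d²/(2R). The limit is reached at d = √(2 × R × 0.010).
- Change in gap at the optic edge ≈ 2.25 × d/R, in opposite directions on the two sides.

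For R = 8 mm, d = √0.16 = 0.40 mm, which is 0.40/4.5 = 9% of the optic. For a 0.25 mm shift at the same R, the central change is 0.0625/16 = 0.0039 mm and the edge change is 2.25 × 0.25/8 = 0.070 mm.

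| R (mm) | Largest shift within the central limit (mm) | Share of optic | Central change at 0.25 mm (microns) | Edge change at 0.25 mm (microns) |
|---|---|---|---|---|
| 8 | 0.40 | 9% | 3.9 | 70 |
| 10 | 0.45 | 10% | 3.1 | 56 |
| 15 | 0.55 | 12% | 2.1 | 38 |
| 20 | 0.63 | 14% | 1.6 | 28 |
| 30 | 0.77 | 17% | 1.0 | 19 |

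On central spacing, an eye with a 0.25 mm shift passes at every radius. If uniformity means the gap across the optic, the same eye fails at every radius, because 19 to 70 microns exceeds 10. The choice between the protocol's and the SAP's wording therefore decides the result for that eye. A lens that slides along a surface of matching curvature, or turns about its own axis, need not change either measure.

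**Step 3. Effect on the reported rate.** One eye out of n moves the percentage by 1/n. With n at most 10, that is at least 10 percentage points per eye, and more within a surgical-technique stratum.

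**The case against.** A reader might infer that nobody checks centration after day 14. The documents do not support that. Malposition, unseated tabs and dislocation are named adverse events, collected at every postoperative visit alongside a slit-lamp examination and tabulated by visit. Adverse event incidence is itself a safety endpoint. A visibly off-centre lens fits the event description and should be reported beside the stability rate. What remains is that these events have no link to the stability count. Nor does the supplied text require a yes/no entry, so the absence of a report does not show that the lens was checked and found centred.

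A reader might also infer that the plan measures only an axial gap. That fits the SAP but not clearly the protocol, whose uniformity wording may respond to shift or tilt. This limits the point to the SAP's count, and it reveals a conflict between the two documents that needs settling anyway.

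The geometry can be challenged too. The radii are assumed, and protocol sections 1 and 9 describe pawls that grip the edge of the host optic. Slippage might need a pawl to release, which could tilt the optic or show as an unseated tab. The shifts in the table are therefore an illustration and not a forecast, and no passage says what decentration distance matters.

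Finally, this is a descriptive early feasibility study of at most 10 eyes, with no pass mark on the stability rate. The two tables can be read together, and nothing says that a feasibility decision rests on the stability rate alone. That lowers the stakes, but the plan still does not say which result answers the primary objective.

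**Conclusion.** The point holds in a limited form. The long-term stability endpoint contains no decentration or rotation criterion, the protocol and SAP define its gap measure differently, and recorded malposition, unseated tabs or dislocation do not count as stability failures. Applied as written, SAP 7.5.3 can count a slipped lens as stable while SAP 7.5.4 reports the same eye as malpositioned.

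The definitional part rests on the text alone. The size, about 0.4 to 0.6 mm of shift within the limit, rests on assumed radii of 8 to 20 mm and movement without tilt. Appendices 3 and 8 (clinical methods and case report forms) were not available, so a centration or orientation field may already exist there. Even so, the endpoint definitions in the supplied text do not use one. The change is worth making because it is cheap and bears on the primary objective.

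**What to change.** 1. In protocol section 2 and SAP 3.2 and 7.5.3, settle on one gap measure. State whether it is central spacing or gap across the optic and, if the latter, at which points it is read.
2. In SAP 3.2 and 7.5.3, count an eye as positionally stable only if the UBM limit holds and no malposition or misalignment, unseated-tab or dislocation event has been recorded up to that visit. Score the existing 7-14-day centration and leaflet-cover items yes/no again at the slit-lamp examinations at Forms 3, 4 and 5 (leaflet cover where visible), so that no report means checked and centred.
3. Report the gap result, the centration result and the composite separately by visit. The gap comparison starts at Form 4, because Form 3 is its baseline. The scheduled 12-month scan can be shown beside it.
4. Either record the orientation of the IOPCL relative to the host lens haptics at those visits, or state that the endpoint does not address rotation.

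The cost is protocol and SAP wording and a few case report form items at existing visits, fewer if Appendices 3 and 8 already contain them. The stated stability rate may come out lower.
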